10.1.3 Expectedness of an AE

An AE that is not included in the Listing of Adverse Drug reactions in the Investigator's Brochure for Abemaciclib, by its specificity, severity, outcome, or frequency, is considered an unexpected AE.

If necessary, Lilly's U.S. Pharmacovigilance Department may assist the Principal Investigator, to determine the expectedness for SAEs especially in the event it is related, unexpected and of special interest.

10.1.4 Relationship of an AE to the Study Drug

The relationship of an AE to the study drug is characterized as follows:

| Term | Definition | Clarification |
|------|------------|---------------|
| | | |

| Term | Definition | Clarification | |
|--------------------------------------------------|-------------------------------------------------------------------------------------------------------------------------------------------------------------------------------------------------------------------------------------------------------------------------|---------------------------------------------------------------------------------------------------------------------------------------------------------------------------------------------------------------------------------------------------------------------------------------------------------------------------------------------------------------------------------------------------------------------------------------------------------------------------------------------------------------------------------------------------------------------------------------------------------------------------------------------------------------------------------------------------------------|--|
| No reasonable possibility (not related) | This category applies to AEs which, after careful consideration, are clearly due to extraneous causes (disease, environment, etc.) or to AEs, which, after careful medical consideration at the time they are evaluated, are judged to be unrelated to the study drug. | The relationship of an AE may be considered "no reasonable possibility" if it is clearly due to extraneous causes or if at least 2 of the following apply: It does not follow a reasonable temporal sequence from the administration of the test drug. It could readily have been produced by the participant's clinical state, environmental or toxic factors, or other modes of therapy administered to the participant. It does not follow a known pattern of response to the test drug. It does not reappear or worsen when the drug is re-administered. | |
| Reasonable possibility (related) | This category applies to AEs for which, after careful medical consideration at the time they are evaluated, a connection with the test drug administration cannot be ruled out with certainty nor felt with a high degree of certainty to be related to the study drug. | The relationship of an AE may be considered "reasonable possibility" if at least 2 of the following apply: It follows a reasonable temporal sequence from administration of the drug. It cannot be reasonably explained by the known characteristics of the participant's clinical state, environmental or toxic factors, or other modes of the the therapy administered to the participant. It disappears or decreases on cessation or reduction in dose. There are important exceptions when an AE does not disappear upon discontinuation of the drug, yet drug-relatedness clearly exists. It follows a known pattern of response to the tendrug. | |

10.1.5 Severity of an AE

The severity of each AE will be graded according to the National Cancer Institute Common Terminology Criteria for AEs, current version 5.0 (NCI CTCAE version 5.0).

AEs that are not included in the NCI CTCAE lists will be graded according to the NCI CTCAE general guideline for grades as follows:

Grade 1: Mild; asymptomatic or mild symptoms; clinical or diagnostic observations only; intervention not indicated

- **Grade 2** Moderate; minimal, local intervention, or noninvasive intervention indicated; limiting age-appropriate instrumental activities of daily living (ADL), e.g., preparing meals, shopping for groceries or clothes, using the telephone, managing money
- **Grade 3** Severe or medically significant but not immediately life-threatening; hospitalization or prolongation of hospitalization indicated; disabling; limiting self-care ADL, e.g., bathing, dressing and undressing, feeding self, using the toilet, taking medications, and not bedridden.
- Grade 4 Life-threatening consequences; urgent intervention indicated
- **Grade 5** Death related to AE

10.2 Serious Adverse Events

10.2.1 Definition of a SAE

A SAE is an AE occurring at any dose that results in any of the following outcomes or actions:

- Death
- A life-threatening AE (i.e., the participant was at immediate risk of death from the event as it
 occurred); does not include an event that, had it occurred in a more severe form, might have
 caused death
- Inpatient hospitalization or prolongation of existing hospitalization means that hospital inpatient admission and/or prolongation of hospital stay were required for treatment of an AE, or that they occurred as a consequence of the event. Hospitalizations scheduled for an elective procedure or for treatment of a pre-existing condition that has not worsened during participation in the study will not be considered SAEs.
- Persistent or significant disability or incapacity (refers to a substantial disruption of one's ability to conduct normal life functions)
- A congenital anomaly or birth defect
- An important medical event that may not result in death, be life-threatening, or require hospitalization, but may jeopardize the participant and may require medical intervention to prevent one of the outcomes listed in this definition. Examples of such events are intensive treatment in an emergency room or at home for allergic bronchospasm; blood dyscrasias or convulsions that do not result in hospitalization; or the development of drug dependency or drug abuse. Note: Any suspected transmission of an infectious agent via a medicinal product is considered an important medical event.

Reportable AEs, UAP, SAEs and Protocol Violation reporting to DSMC

| Type of Event | To whom will it be reported | Time Frame for Reporting | How to report? |
|---------------|-----------------------------|--------------------------|----------------|
| | reported | Keporting | |

| Death of a research participant unless the death is expected (e.g., due to disease progression). | PSCI DSMC and designated IRB, if applicable per IRB policy. | DSMC: Within 24 hours | DSMC: Email to PSCI- [contact] |
|---------------------------------------------------------------------------------------------------|-------------------------------------------------------------|--------------------------------------------------------------------------------------------|------------------------------------------------------|
| Serious Adverse Event, regardless of relatedness of expectedness | PSCI DSMC and designated IRB, if applicable per IRB policy. | DSMC: Within 10 working days from the time the study team received knowledge of the event. | DSMC: Email to PSCI- [contact] |
| Unanticipated Problems that are not adverse events or protocol deviations | PSCI DSMC and designated IRB, if applicable per IRB policy. | DSMC: Within 10 working days from the time the study team received knowledge of the event. | DSMC: Email to PSCI- [contact] |

10.3 Reporting of AEs and SAEs

10.3.1 Investigator Responsibility

An unanticipated AE is one that is deemed to be unexpected and related (reasonable possibility) to the investigational medication. All unanticipated AEs that occur during the protocol specific AE observation time period must be reported to the Principal Investigator immediately. If a serious unexpected AE is believed to be related to the study drug or study procedures, the Principal Investigator will take appropriate steps to notify all the appropriate regulatory authorities.

All SAEs will be reported to the sponsor within 24 hours of knowledge. SAEs will be reported to the sponsor using the MedWatch Form 3500A. Updates to the SAE should be made as events change.

The Sponsor-Investigator will submit a written IND Safety Report (i.e., completed FDA Form 3500A) to the responsible new drug review division of the FDA for any observed or volunteered adverse event that is determined to be a serious and unexpected, suspected adverse reaction. Each IND Safety Report will be prominently labeled, "IND Safety Report", and a copy will be provided to all participating investigators (if applicable) and sub-investigators.

Written IND Safety Reports will be submitted to the FDA as soon as possible and, in no event, later than 15 calendar days following the Sponsor-Investigator's receipt of the respective adverse event information and determination that it meets the respective criteria for reporting.

For each written IND Safety Report, the Sponsor-Investigator will identify all previously submitted IND Safety Reports that addressed a similar suspected adverse reaction experience and will provide an analysis of the significance of newly reported, suspected adverse reaction in light of the previous, similar report(s) or any other relevant information.

Relevant follow-up information to an IND Safety Report will be submitted to the applicable review division of the FDA as soon as the information is available and will be identified as such (i.e., "Follow-up IND Safety Report").

If the results of the Sponsor-Investigator's follow-up investigation show that an adverse event that was initially determined to not require a written IND Safety Report does, in fact, meet the requirements for reporting; the Sponsor-Investigator will submit a written IND Safety Report as soon as possible, but in no event later than 15 calendar days, after the determination was made.

In addition to the subsequent submission of a written IND Safety Report (i.e., completed FDA Form 3500A), the Sponsor will notify the responsible review division of the FDA of any unexpected, fatal or life-threatening suspected adverse reaction.

The telephone or facsimile transmission of applicable IND Safety Reports will be made as soon as possible but in no event later than 7 calendar days after the Sponsor-Investigator's receipt of the respective adverse event information and determination that it meets the respective criteria for reporting.

Unexpected and related AEs as defined by Penn State IRB (regardless of grades) and SAEs will be reported to the Penn State IRB expeditiously per their requirements. The study funder, Eli Lilly, will be notified within one business day of Investigator and/or Institution receiving notification of any "serious" adverse event experienced by a patient participating in the Study and receiving Study Drug. For purposes of this requirement, "serious" means: (1) death; (2) in-patient hospitalization or prolonged hospitalization; (3) life-threatening; (4) persistent or significant disability or incapacity; (5) congenital anomaly or birth defect; or (6) other serious events that may jeopardize the patient and may require medical or surgical intervention to prevent one of the other five listed outcomes. Serious adverse events should be reported to Lilly using a MedWatch 3500A Form ([contact]). Investigator and Institution further agree to make available promptly to Lilly such records as may be necessary and pertinent for Lilly to further investigate an adverse event in the Study that is possibly associated with the Study Drug.

Based on the unanticipated toxicity, the Sponsor/Investigator, [name] may take the following steps where applicable:

- Amending the current protocol
- Discontinuing or suspending the study
- Altering the process of informed consent by modifying the existing informed consent form and informing current study participants of any new findings. This includes modifying listings of expected toxicities to include AEs newly identified as related to the study medication.

The Principal Investigator must ensure that the IRB and DSMC are also informed of the event, in accordance with local regulations.

10.4 Pregnancy

All pregnancies (pregnancies of women participating in the study and partners of men participating in the study) that occur during the study, or 30 days after last dose of the study drug, are to be reported immediately to the individual identified in the clinical study personnel contact information section of this protocol, and the Principal Investigator must provide the Eli Lilly's USA Pharmacovigilance Department with MedWatch 3500A form ([contact]). Although pregnancy is not a SAE, the process for reporting a pregnancy is the same as that for reporting a SAE.

Any participant becoming pregnant during the study will be withdrawn. All participants (or partners) who become pregnant will be monitored to the completion or termination of the pregnancy. If the pregnancy continues to term, the outcome (health of the infant up to 8 weeks of age), including spontaneous or voluntary termination, details of birth, and presence or absence of any birth defect, congenital abnormalities, or maternal and newborn complications, will be reported to Eli Lilly. Any complication of pregnancy will be reported as an AE or SAE, as appropriate.

If the pregnancy does not continue to term, 1 of the following actions will be taken:

- For a spontaneous abortion, report as a SAE.
- For an elective abortion due to developmental anomalies, report as a SAE.
- For an elective abortion not due to developmental anomalies, report on the pregnancy form.

11.0 STUDY MONITORING, AUDITING, AND INSPECTION

11.1 Protocol Amendments

No changes from the final approved protocol will be initiated without the prior written approval or favorable opinion of a written amendment by the IRB/IEC, except when necessary to address immediate safety concerns to the participants or when the logistical or administrative changes are required.

11.2 Information to Study Personnel

The Principal Investigator is responsible for administering information about the study to all staff members involved in the study or in any element of participant management, both before starting the study and during the course of the study (e.g., when new staff become involved). The Principal Investigator must assure that all study staff members are qualified by education, experience, and training to perform their specific responsibilities. Study staff members must be listed on the Delegation of Authority Log, which includes a clear description of each staff member's responsibilities. This list must be reviewed and updated throughout the study, as necessary.

The Principal Investigator is responsible for explaining the protocol to all study staff, including any sub-investigators, and for ensuring they comply with the protocol. Additional information will be made available during the study when new staff becomes involved in the study.

At monthly intervals, routinely scheduled meetings with the study staff members will be conducted at the Penn State Cancer Institute. All sub-Investigators and study staff members will be notified of new information regarding the safety of the study drug and presented updates on the study. Written documentation of such notifications will be maintained in the regulatory files of the Clinical Trials Office.

11.3 Study Monitoring

The Principal Investigator will ensure that this study is conducted and that the data are collected, documented, and reported in compliance with this protocol, federal regulations, institutional and IRB policies and procedures. Good Clinical Practice guidelines and any other applicable regulatory requirements. The study will be monitored by the PSCI Quality Assurance Department. The monitors will provide an independent review of the regulatory and subject records and associated data collected to assure appropriate compliance, ensuring human subject's protection, examine the quality, reliability, and integrity of data collected and provide opportunities for corrective action while the study is ongoing. Comprehensive monitoring will be conducted by a PSCI Quality Assurance monitor specifically for the PSCI-CTO and planned visits will start at Site Initiation Visit (SIV), a visit will take place within two weeks after the first subject receives protocol treatment; every 6-8 weeks until the last subject is enrolled, and thereafter every 4-6 months until all subjects have come off active treatment. Once all subjects are on long term follow-up monitoring visits will occur annually; the remaining visits will happen for close out; and ad-hoc for any study based on findings.

The investigational site will provide direct access to all trial-related sites, source data/ documents, and reports for the purpose of auditing by the DSMC, and inspection by local and regulatory authorities.

11.4 Audit and Inspection

The Principal Investigator will allow for auditing and inspecting by all applicable federal, state and local entities at any time. Lilly Pharmaceuticals, the pharmaceutical manufacturer of abemaciclib who is providing funding for this study, may audit the investigational center to evaluate study conduct and compliance with protocols, SOPs, GCPs, and applicable regulatory requirements. The Quality Assurance Unit at Lilly, independent of the PSCI Quality Assurance will be responsible for determining the need for (and timing of) an investigational center audit.

The Principal Investigator and Sub-Investigators must accept that regulatory authorities and Eli Lilly representatives may conduct inspections to verify compliance of the study with GCP guidelines.

The DSMC, study monitors from Penn State Cancer Institute Quality Assurance Department, any auditors, the PSCI IRB, or any other health authority inspectors (or their agents) will be given direct access to source data and documentation (e.g., medical charts/records, laboratory test results, printouts, videotapes) for source data verification, provided that participant confidentiality is maintained.

The Principal Investigator and any Sub-investigator must maintain all original source documents of each participant's data at all times. Examples of source documents are hospital records, office visit records, examining physician's finding or notes, consultant's written opinion or notes, laboratory reports, drug inventory, study drug label records, diary data, protocol required worksheets, and eCRFs that are used as the source.

12.0 DATA HANDLING, DATA QUALITY ASSURANCE, AND RECORD KEEPING

12.1 Data Collection

Direct data entry into to the Penn State Cancer Institute OnCore CTMS will be utilized for this study. In addition to demographics, medical history, concomitant medications, and safety data, only those data needed to answer the study objectives will be included in the study database. The assessments and interventions noted in the *Protocol Required Interventions and Assessments* (Appendix B) will not be entered into the database. This data includes dates and results of physical examinations, vital signs, performance status, and laboratory results (CBC, Chemistry). Any abnormal results of the assessments will be captured as an AE according to the criteria noted in Section 10. Any concomitant medications administered for the purpose of procedures (anesthetics, etc.) will not be included in the data collection. AEs and SAEs will be recorded after the start of study drug until 30 days after discontinuation of study drug(s) or until a new anti-cancer treatment starts, whichever occurs first. AE that are ongoing at time will be checked or ongoing with no stop date. Unanticipated SAEs (ie. Serious, unexpected, and related (even remotely)) will be reported on the SAE Submission Form and entered in Oncore within 1 business day of discovery of the event. All other SAEs will be entered in the Oncore system within 5 business days. For screen failures (participants who sign the informed consent form but do not meet eligibility criteria), data relating to failure reason and demography will be captured.

Data will be reviewed for consistency by Data Management using both automated logical checks and manual review. The data collected will be reviewed and approved by the Principal Investigator or designated Co-investigator on an approximately quarterly basis depending on enrollment. Evidence of the Principal Investigator or Co-investigator review and approval may be done electronically in the OnCore CTMS. This approval acknowledges the Principal Investigator's review and acceptance of the data as being, to the best of his knowledge, complete, accurate, and current per the date documented on the form. Data will be verified using source documentation by the Study Monitor.

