8.5 Safety Variables and Analysis

8.5.1 Safety Variables

The safety and tolerability of abemaciclib treatment will be assessed throughout the study by evaluating AEs.

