8.5.2 Safety Analysis

The safety analysis set will be used for all safety analyses.

All AEs will be graded by CTCAE v 5.0. Summaries will be presented for all AEs (overall and by severity), AEs determined by the investigator to be related or not related to study treatment (overall and by severity), SAEs, serious treatment-related AEs, AEs leading to withdrawal, and Grade 3 and 4 AEs. Participant listings of AEs, SAEs, Grade 3 and 4 AEs, and AEs leading to withdrawal will be presented.

The number and percentage of participants with Grade 3 or 4 values will be tabulated. Summaries of laboratory values for laboratory parameters will be completed as applicable. Vital signs abnormalities will be categorized and tabulated. Summaries of the vital signs measurements will be provided.

The use of concomitant medications will be summarized by therapeutic class using descriptive statistics. Concomitant medications will include all medications taken while the participant is treated with study drug.

For continuous variables, descriptive statistics (n, mean, standard deviation, standard error, median, minimum, and maximum) will be provided for actual values and changes from baseline to each time point. For categorical variables, participant counts and percentages will be provided. Descriptive summaries of SAEs, participant withdrawals due to AEs, and potentially clinically significant abnormal values (clinical laboratory or vital signs) based on predefined criteria will also be provided.

If any participant dies during the study, a listing of deaths will be provided and all relevant information will be discussed in the participant narrative.

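### Section 12.1 keeps out of the database results that 8.3.2 and 8.5.2 plan to tabulate, and the Appendix B post-treatment adverse-event row conflicts with the collection rules in the text

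*Combined protocol and SAP*

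**What the plan says.** **Database scope.** Section 12.1 sets out what is entered: "In addition to demographics, medical history, concomitant medications, and safety data, only those data needed to answer the study objectives". Of the scheduled assessments it then says "Appendix B) will not be entered into the database", and it names what this covers: "This data includes dates and results of physical examinations, vital signs, performance status, and laboratory results (CBC, Chemistry"). Abnormal results are to be captured as AEs if they meet the Section 10 criteria.

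**Planned outputs.** Section 8.5.2 plans four things:
- a count by grade: "The number and percentage of participants with Grade 3 or 4 values will be tabulated"
- a table of out-of-range measurements: "Vital signs abnormalities will be categorized and tabulated"
- a description of the blood and chemistry results: "Summaries of laboratory values for laboratory parameters will be completed as applicable"
- statistics for continuous measures, which "will be provided for actual values and changes from baseline to each time point"

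It also promises summaries of the vital-sign measurements. Section 8.3.2 adds a baseline summary of ECG and physical-examination findings. Section 1.3.3 counts laboratory, vital-sign, ECG, ECOG and examination results among the safety endpoints. Section 8.5.1 is narrower: "The safety and tolerability of abemaciclib treatment will be assessed throughout the study by evaluating AEs".

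**AE collection.** The on-treatment table of Appendix B marks AEs at every visit without restriction. In the post-treatment table the AE row is marked under EOT, the Long-Term Follow-Up cell is blank, and the instruction confines collection to events that are unresolved, drug-related and Grade 3 or higher. Section 7.2.3 lists AEs as an EOT procedure without limit and refers to 10.1.2. Section 10.1.2 collects AEs from Cycle 1 Day 1 through the EOT visit. Section 12.1 records AEs for 30 days after stopping drug, or until a new anti-cancer treatment if that is earlier.

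**The concern.** Confirming tolerability is a stated aim in 8.0. If 12.1 is followed as written, the database will not hold the dated values behind several planned safety tables, and no section describes extracting them from source for analysis. If site staff follow the Appendix B row as written, a new, unrelated or Grade 1–2 event found at EOT is not collected, although three sections of the text require it. The first problem can be repaired later from source. The second acts at the moment of collection, so a non-serious event that nobody records at EOT may not be recoverable.

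**Working it through.** No figure in the plan has to be reproduced; the check sets the passages side by side. The only arithmetic concerns the AE windows, the entry workload and one illustration.

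**1. Can what is entered supply what is planned?** The stated routes into the database are AEs (from Cycle 1 Day 1; earlier events go to medical history, 10.1.2), medical history, and results recorded on the CRF at unscheduled visits (7.2.5).

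| Planned output | Needs | Supplied by those routes? |
|---|---|---|
| Vital-sign summaries and change from baseline (8.5.2) | All dated values, including baseline | No |
| Laboratory summaries and change from baseline (8.5.2) | All dated values, including baseline | No |
| Participants with Grade 3 or 4 values (8.5.2) | Every graded result | In part: only those meeting the AE criteria |
| Vital-sign abnormalities (8.5.2) | Every value, checked against criteria | In part, same reason |
| Baseline examination findings (8.3.2) | Screening examination results | In part: some abnormalities as medical history |

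The AE criteria themselves differ. Section 10.1.2 admits an abnormal laboratory value only if it causes signs or symptoms or needs treatment or further tests. Section 10.1.1 also admits values that lead to withdrawal or that the investigator judges clinically significant. Neither supplies means or changes. ECG is not in the named list in 12.1, but it is an Appendix B assessment and so falls under the general exclusion.

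**2. Are AE reports a fair proxy for laboratory values?** Section 2.4.2 gives both for MONARCH 1, at the same 200 mg twice-daily starting dose (Tables 3 and 4). Grade 3 leukopenia is 5% as an adverse reaction, and Grade 3 white-cell decrease is 28% by laboratory value. Creatinine increase of any grade is 13% against 98%. Grade 3 anemia runs the other way, 5% against 0%. For 10 participants the white-cell figures correspond to 10 × 0.05 = 0.5 against 10 × 0.28 = 2.8 participants. This is illustration only: that study's AE rules may differ from this one's. It shows that the two sources are not interchangeable and that the direction of the difference cannot be assumed.

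**3. AE collection at EOT, two readings of the row.**
- It governs EOT, where it is marked. It then conflicts with 7.2.3, 10.1.2 and 12.1, none of which limits grade or causality.
- It was meant for follow-up after EOT. It then conflicts with 10.1.2, which follows ongoing related AEs of any grade to resolution, baseline or Grade 1, with no Grade 3 floor.

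**4. End of the collection window.** Section 3.4.1 puts EOT at 30 ± 7 days after last treatment, that is day 23 to day 37. Against day 30 in 12.1 the difference is 23 − 30 = −7 to 37 − 30 = +7 days. The late side shrinks if EOT is at most about 30 days after last dose, as 10.1.2 says. But 12.1 also stops at a new anti-cancer treatment. If that starts on day t before day 30, the difference becomes 23 − t to 37 − t days, so ±7 days is not a bound. If the final evaluations are done on the last dosing day, which 7.2.3 offers as an alternative, and collection is taken to end there, the gap is about 30 days.

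**5. Entry workload (Appendix B).** Eight cycles: screening 1 + cycles 1–2 4 + Day 1 of cycles 3–8 6 + EOT 1 = 12 time points. With hematology, chemistry and vital signs at each, 12 × 3 = 36 records per participant, or 360 for 10 and 720 for 20. Stopping at C3D1: 1 + 4 + 1 + 1 = 7 time points, 7 × 3 = 21 records, or 210 to 420. Unscheduled tests, treatment beyond cycle 8, coagulation, urinalysis and CA 19-9 are not counted.

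**The case against.** The best defense of the database rule is that 12.1 admits safety data in general terms, that abnormal results enter as AEs, and that laboratory summaries are promised only as applicable. Part of this stands. Grade 3 or 4 hematologic toxicity requires a dose hold under 7.3.8, so many such values would probably reach the AE record, and medical history could carry baseline abnormalities. But the general phrase is followed directly by an exclusion that names these results, and the as-applicable qualifier does not reach the vital-sign or change-from-baseline summaries.

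A reader might infer that the safety values are lost. The documents do not support that: results stay in source, with access described in 11.3 and 11.4 for audit and verification, and 8.6 says data requested early by the DSMC will be cleaned and provided. What is missing is a described extraction for the 8.3.2 and 8.5.2 tables.

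On AEs, the limit may be misplaced follow-up text. The imaging row of the same table is also marked under EOT yet carries an instruction that starts three months after last dose. That reading is plausible, but the Long-Term Follow-Up cell is blank, and the conflict with 10.1.2 remains either way. It is also fair that 10.1.2 requires every AE in the study period to be recorded in source, so an omission requires staff to follow one table cell against three sections.

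A reader might also infer that AE collection is restricted throughout the study. It is not: the on-treatment row carries no limit.

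**Conclusion.** Both contradictions are in the text and should be corrected. Under 12.1 as written, the entered data cannot supply the vital-sign and laboratory summaries, the changes from baseline, or a complete count of Grade 3 or 4 values. The post-treatment AE row conflicts with the text on either reading. If it is applied at EOT, the risk is under-collection of non-serious events; serious events remain reportable under 10.3.1.

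The effect is confined to descriptive safety results. It does not touch the response rate, and nothing here suggests the primary result is at risk. The record counts measure workload, not bias. The documents give no AE rate for the period after the last dose, so the number of events that might be missed is not estimated. The conclusion assumes that the named exclusion in 12.1 prevails over its general mention of safety data, which the plan leaves unsaid.

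**What to change.** 1. Amend 12.1 so that the dated laboratory, vital-sign and baseline examination results needed for 8.3.2 and 8.5.2 are entered in or exported to the database, and say whether safety data covers them. Align 8.5.1, 8.5.2 and 1.3.3, including ECOG, which 1.3.3 lists but 8.5 does not tabulate.
2. In the Appendix B post-treatment table, remove the grade and relatedness limit from AE collection at EOT. State any follow-up rule after EOT separately and consistently with 10.1.2.
3. Reconcile 7.2.3, 10.1.2, 12.1 and Appendix B into one collection window that loses no event now collected under 10.1.2. The later of the EOT visit and 30 days after last dose is one wording that would do so. State whether the new-anti-cancer-treatment cut-off applies.

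Cost: entry or export of results already in source, about 360 to 720 scheduled hematology, chemistry and vital-sign records if 10 to 20 participants complete eight cycles (fewer if they stop early), plus 10 to 20 baseline examination records and any unscheduled or later assessments included. The Appendix B correction is one line and adds AE entry at a visit already scheduled. The rest is text amendment.
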